- Receive at least 70% of the planned study drug in Period 1 for subjects who complete Period 1 or receive at least one dose of study drug and discontinue Period 1
- Provide at least one post Baseline assessment on lesion count
- Meet the Hurly stage II: Total SCAR and Fistula counts > 0 at either screening or Day 1.
- Have Baseline AN count ≥ 3
- Have Baseline draining fistula count ≤ 20
- Do not take the following exclusionary medications during the exclusionary screening period or during Period 1:
- Any concomitant antibiotics for the treatment of HS (except the protocol allowed rescue medication which will result in counting the subjects as non-responders, or having the last observation prior to the use of these treatments carried forward).
- Anti-TNF-a (Humira), Methotrexate (MTX), cyclosporin, corticosteroids, and retinoids for any reason, or other medication for treatment of their HS that will confound the efficacy evaluation (to be determined and documented in the classification results prior to blind break).

Per-Protocol Population in Period 2 (PP2) will be defined separately.

Subjects included in the Per-Protocol Population will be analyzed as treated. That is, if a subject receives the treatment that is not the randomized assignment during their entire participation of a period, the subject will be analyzed according to the treatment that the subject actually received in the period.

Safety Population

The Safety Population will include all subjects who are randomized and have received at least one dose of study drug, excluding those subjects who are from study Site 138. Due to the reasons stated above safety data of subjects from site 138, including adverse events, will be listed separately only and not be included in the summary tables:

- The Safety Population in Period 1 (Safety1) is defined as all subjects who are randomized at baseline and have received at least one dose of study drug during Period 1.
- The Safety Population in Period 2 (Safety2) is defined as all subjects who
 received at least one dose of avacopan during Period 2.
- The All Avacopan Treated Population is defined as all subjects who receive at least one dose of avacopan in any treatment period.

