The DLQI is calculated by adding the score of each question. The maximum score is 30, and the minimum score is 0. The higher the score, the more quality of life is impaired.

Meaning of DLQI Scores

0-1 = no effect at all on subject's life

2-5 = small effect on subject's life

6-10 = moderate effect on subject's life

11-20 = very large effect on subject's life

21-30 = extremely large effect on subject's life

Change from Baseline in Score = Post Baseline Score - Baseline Score

8) Proportion of subjects who experienced flare, defined by at least a 25% increase in AN counts with a minimum increase of 2 AN counts relative to Baseline

The AN count is the sum of all abscesses and inflammatory nodules counts across all regions.

% Increase in AN counts

$$= 100 \times \frac{\text{(AN Counts at Day x} - \text{AN Counts at Baseline)}}{\text{AN Count at Baseline}}$$

The proportion of subjects who experienced flare at Post Baseline visits will be calculated as those subjects having % Increase in AN counts ≥ 25 and (Post Baseline AN Counts – Baseline AN Counts) ≥ 2 at Post Baseline visits divided by the total number of subjects in each treatment group.

9) Duration of flare in days (Observed case only)

> Duration of flare in days is calculated from the day when flare is observed to the day prior to the observation that flare is no longer present; of note, there could be multiple periods that flares are observed, in which case, the total days from the multiple periods will be used.

10) Proportion of subjects who experience at least 25% increase in draining fistula counts with a minimum increase of 2 draining fistula counts relative to Baseline.

% Increase in Draining Fistula Counts

The proportion of subjects who experienced at least 25% increase in draining fistula counts with a minimum increase of 2 draining fistula counts relative to Baseline at Post Baseline visits will be calculated as those subjects having % Increase in Draining Fistula Counts > 25 and

(Post Baseline Draining Fistula Counts —

Baseline Draining Fistula Counts) ≥ 2 at Post Baseline visits divided by the total number of subjects in each treatment group.

11) During Period 2, proportion of subjects with a loss of response, (LOR) defined as loss of at least 50% of AN count improvement achieved at Week 12 from Period 1.

AN in Period 2 – Week 12 AN $> \frac{1}{2}$ (Baseline AN – Week 12 AN)

i.e., AN in Period 2 > $\frac{1}{2}$ (Baseline AN +Week 12 AN)

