Proportion of subjects with a LOR in Period 2 is calculated as those subjects having AN Counts in Period 2 $> 0.5 \times$ (Baseline AN counts —Week 12 AN counts) divided by the total number of subjects in each treatment group in Period 2.

12) Time to LOR during Period 2.

For subjects with LOR, time to LOR (days) = date of LOR – date of the first dose of study drug in Period 2 + 1; For Subjects without LOR or lost follow-up, subjects will be censored at the date of the last assessment of number of HS lesions, i.e., time to LOR (days) = date of last assessment of number of HS lesions – date of the first dose of study drug in Period 2 + 1.

 Proportion of subjects who received add-on antibiotic or other therapy for HS during Period 1 and Period 2 separately.

Add-on antibiotic or other therapies for HS are captured in the Concomitant Medication CRFs.

Proportion of subjects who received add-on antibiotic or other therapy will be calculated as those subjects who received add-on antibiotic or other therapy documented in the CM CRF post baseline divided by the total number of subjects in each treatment group in the safety population.

14) Proportion of subjects who start disallowed opioid pain therapy during Period 1 and Period 2 separately.

Oral and transdermal opioid analgesics (except for tramadol) for any reason are disallowed. Disallowed opioid pain therapy are captured in the Concomitant Medication (CM) CRFs.

Proportion of subjects who start disallowed opioid pain therapy will be calculated as those subjects who start disallowed opioid pain therapy documented in the CM CRF post baseline divided by the total number of subjects in each treatment group in safety population.

15) Proportion of subjects who undergo lesion intervention due to HS during Period 1 and Period 2 separately.

Lesion intervention due to HS is collected in AE and Concurrent Procedures CRFs.

Only two types of interventions are allowed: injection with intralesional triamcinolone acetonide suspension (intralesional Kenalog® rescue injections, i.e., triamcinolone acetonide, 10 mg total maximum per subject within a period no longer than 1 week) and incision and drainage. Any disallowed lesions interventions due to HS other than the two types described above will also be counted as "Lesion intervention due to HS" and will be recorded as major (=CSR reportable) protocol deviation.

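### SAP item 11 prints two loss-of-response thresholds that differ by exactly the Week 12 AN count, and neither requires an improvement at Week 12

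*SAP*

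**What the plan says.** SAP VIII.B, item 11, first states LOR in words: "defined as loss of at least 50% of AN count improvement achieved at Week 12 from Period 1". It then gives a formula, "AN in Period 2 – Week 12 AN $> \frac{1}{2}$ (Baseline AN – Week 12 AN" (closing bracket cut), and a rearrangement, "i.e., AN in Period 2 > $\frac{1}{2}$ (Baseline AN +Week 12 AN" (closing bracket cut). The next sentence, which says how the proportion is to be computed, counts subjects with "AN Counts in Period 2 $> 0.5 \times$ (Baseline AN counts —Week 12 AN counts) divided by the total number of subjects". The denominator is everyone in the arm: "divided by the total number of subjects in each treatment group in Period 2".

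Item 12 (time to LOR) has no event rule of its own. It says "For subjects with LOR, time to LOR (days) = date of LOR" and dates the event from the first Period 2 dose; for subjects without LOR, "subjects will be censored at the date of the last assessment of number of HS lesions".

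Protocol 8.5.3, item 10, gives the same verbal definition, with the improvement measured from Day 1 to Week 12, and no formula. Protocol 4.4 sets no response requirement for entering Period 2. SAP VI.I treats comparisons on the other efficacy endpoints as supportive or exploratory. SAP VIII.E (Period 2) summarises the proportion descriptively in ITT2 and tests time to LOR with a stratified log-rank test in four pairwise comparisons.

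**The concern.** The definition and the calculation sentence use different thresholds, and the SAP does not say which prevails. The calculation sentence is the operational one, so it could be what gets programmed. It would then report as losses many subjects who held their Week 12 gain or improved on it, including some who still meet the AN part of HiSCR.

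The words also presuppose an improvement that can be lost, but no formula requires one. Subjects who were worse at Week 12 than at Baseline can therefore be classed as losing a response they never had. At stake is the meaning of the LOR proportion and, because item 12 relies on item 11 for its event, the clarity of the time-to-LOR analysis.

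**Working it through.** **Inputs.** B = Baseline AN, W = Week 12 AN, A = AN at a Period 2 visit. The rules are those printed in SAP VIII.B, item 11. No AN distribution is assumed, because the documents give none.

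**1. Reproduce the SAP's own rearrangement.** A − W > ½(B − W). Adding W to both sides gives A > ½B + ½W = ½(B + W). The SAP's two definition lines agree, and apart from exact midpoints they match the words.

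**2. Compare with the calculation sentence.** It uses A > ½(B − W). The gap between thresholds is ½(B + W) − ½(B − W) = W. The two rules coincide for every A only when W = 0.

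**3. Numbers.**

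| B | W | Definition, ½(B + W) | Calculation, ½(B − W) |
|---|---|---|---|
| 12 | 6 | 9 | 3 |
| 20 | 8 | 14 | 6 |
| 10 | 5 | 7.5 | 2.5 |
| 10 | 10 | 10 | 0 |
| 10 | 14 | 12 | −2 |

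In the first row, a subject who stays at 6, or falls further to 4, is a loss by the calculation sentence and not by the definition.

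**4. Stable subjects (A = W).** The calculation sentence flags them when W > ½(B − W), i.e. 3W > B, i.e. W is more than one third of B. That is any Week 12 reduction below 66.7%. A subject at exactly a 50% reduction has W = 0.5B and a threshold of 0.25B, so the count must fall to a 75% reduction to avoid being a loss.

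**5. Worse at Week 12 (W > B).** The calculation threshold is negative, so A = 0, complete clearance, is a loss.

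**6. Enumeration.** Over B = 3 to 40, W = 0 to 60 and A = 0 to 60 there are 38 × 61 × 61 = 141,398 combinations. The two definition lines never disagree. The calculation sentence alone flags 55,043 combinations, and the definition alone flags none. Among the 49,837 combinations with W < B, 10,659 are classified differently. These count grid points and are not expected frequencies.

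**7. No improvement required.** With B = 10, W = 14, A = 13, the definition threshold is 12 and 13 > 12, so the subject is LOR. Yet nothing was gained by Week 12 and the count has fallen since.

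**8. The inequality sign.** With B = 10, W = 4, A = 7, the loss is 3 of 6, exactly half. The words (at least 50%) make this a loss, but 7 > 7 is false. Changing > to ≥ alone would flag B = W = A = 10, an unchanged subject. With the added condition W < B, a stable subject is never flagged, because W ≥ ½(B + W) would need W ≥ B.

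**The case against.** The strongest reply is that the intended rule is plain from the lines just above. The words, both definition formulas and the protocol wording all point to the midpoint threshold, and a careful programmer would follow them. That is likely, but the SAP prints a contrary expression in the sentence that describes the calculation and states no precedence.

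A second reply is that the fault may lie in the PDF reading. It cannot be excluded. The printed expression has the same structure as the second definition line with the plus replaced by a long dash, so a wrong or misread sign explains it at least as well as a dropped Week 12 term. The SAP does use a long dash as a minus elsewhere, in the HiSCR formula. The cause does not change the threshold as printed.

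Some stronger readings are tempting but not supported:

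- A reader might infer that the log-rank analysis is wrong. Item 12 refers to subjects with LOR, and LOR is defined by the earlier lines of item 11. The faulty expression is written only for the proportion. Item 12 is therefore ambiguous at most.
- A reader might infer a bias towards one arm. Placebo starters move to avacopan at Week 12, so any direction depends on how they then respond.
- A reader might count the > versus at-least mismatch as a second error. It matters only at exact midpoints and may be a lost symbol: item 10 of the same list shows the same mismatch, while the parallel item 8 prints ≥.
- A reader might take the Period 1 per-protocol criterion, "Have Baseline AN count ≥ 3", as a floor on Baseline counts here. It does not apply to ITT2.

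**Conclusion.** Item 11 contradicts itself as printed. The calculation threshold is below the defined one by exactly the Week 12 count. The misclassification in steps 3 to 5 follows only if the calculation sentence is the one programmed. The missing improvement requirement is a separate, smaller gap that remains even under the definition lines.

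The result is exact algebra on the printed rules. No LOR rate or treatment-group difference is estimated. Severity is minor: LOR is an exploratory endpoint outside the testing hierarchy, its proportion is descriptive, and the primary and ranked secondary analyses do not use it.

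**What to change.** In the calculation sentence of item 11, replace the expression with 0.5 × (Baseline AN + Week 12 AN). Add the condition Week 12 AN < Baseline AN to the event, in the definition lines as well. State in item 12 that time to LOR uses this same event. Check the inequality sign against the source file, and use ≥ only together with the improvement condition. Keep the present denominator and censoring rule.

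The cost is one expression, one condition and one sentence, with no new data.

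The downside should be stated. Subjects without a Week 12 improvement stay in the denominator and in the log-rank risk set but cannot have the event. Both the proportion and the comparisons in SAP VIII.E then partly reflect how many improved by Week 12, and an arm with fewer improvers could look better at keeping its response. Show both results also among subjects who improved, labelled descriptive because this selects on a post-randomisation outcome. A minimal improver can still be LOR on one lesion: Baseline 12 and Week 12 count 11 give a threshold of 11.5.

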- Follow-up Period (8 weeks)

Subjects will be screened for eligibility based on the stage of the disease and their health status. The screening period will be up to 28 days. The primary efficacy analysis will occur when the last enrolled subject has completed the Week 12 visit. After the blinded 12-week treatment period, all subjects will continue an additional 24-week treatment with either 10 mg or 30 mg avacopan twice daily. The treatment assignment to 10 mg or 30 mg twice daily will not be disclosed to the subject, study personnel at the site or the sponsor. Thereafter, all subjects will be followed for 8 weeks.

B. Study Population

Eligible adult subjects (at least 18 years of age) with moderate to severe hidradenitis suppurativa (Hurley stage II or III) on standard-of-care therapy as specified by the inclusion and exclusion criteria in the protocol Section 4, are allowed to enter the study.

C. Sample Size Estimation

The study will enroll approximately 390 subjects. In two Phase 3 clinical trials with adalimumab (PIONEER I and II; Kimball et al, 2016a), the proportions of subjects in the placebo control group achieving a HiSCR at Week 12 were 26.0% and 27.6%, respectively. Hence, if the control group only receives placebo, one may assume an HiSCR at Week 12 of approximately 30%. The average HiSCR at Week 12 in the adalimumab groups in PIONEER I and II were 41.8% and 58.9%, respectively with an average of approximately 50% (Kimball et al, 2016a). The attrition rate throughout the trial is estimated to be approximately 7%. A sample size of approximately 130 subjects per treatment group (390 in total) at a type I error rate of $\alpha = 0.05$ (two-sided) provides approximately 90% power to detect a 20% superiority of avacopan compared to the placebo control group in HiSCR at Week 12, assuming an HiSCR at Week 12 of 50% in the avacopan group.

D. Treatment Randomization

[figure not shown]
Subjects will be randomized 1:1:1 to one of the three treatment groups within each stratum based on a non-dynamic, list-based blocked randomization scheme

receive 10 mg avacopan twice daily, 30 mg avacopan twice daily or matching placebo for 12 weeks in a double-blind, placebo-controlled manner stratified by:

- 1) Hurley stage (Stage II vs III)
- 2) Concomitant antibiotic therapy (Yes vs No)
- 3) Anti-TNF-α treatment (Treatment naive vs Previous treatment)

E. Assessment Schedule

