Data collected at all visits will be included in the data listings with visit presented as reported by the site.

C. Missing Data

Imputation for Efficacy variables:

The approaches listed below will be used for handling missing data:

- Non-responder imputation (NRI): Subjects who have missing data at the time point of interest are treated as though they did not respond to the treatment.
- Last Observation Carried Forward (LOCF): The LOCF analyses will use
 the last observed non-missing evaluation (last completed non-missing
 evaluation, from composite endpoint) from the previous visit within the
 particular period for efficacy measures assessed to impute missing data at
 later visits in the same period. Baseline efficacy evaluations will not be

carried forward. LOCF will be the primary approach in the analysis of continuous variable.

- Observed case (OC): Missing data are not imputed. Only subjects with available data at the given time point are considered.
- Multiple Imputation (MI) Markov Chain Monte Carlo (MCMC) imputation: Using multiple imputation methodology, missing data in Period 1 are imputed based on the MCMC method, please see Section VIII D for details

The following table depicts which missing data handling approaches should be used based on variable priority (primary, secondary, other) and variable type (binary, continuous).

		Missing Data Handling Approach					
Endpoints	Variable Type	NRI	MI	LOCF	ос		
Primary Efficacy	Binary	P	SEN	SEN			
Primary Efficacy (COVID-19)	Binary	P		SEN			
Secondary/ Other Efficacy	Binary	P	SEN				
(selected ones only, see Page 47)	Continuous			P1	SEN		

P=Primary method, SEN=Sensitivity method

Imputation for AE and Concomitant Medication Start Dates:

For analyses of AEs and concomitant medication usage, a complete date must be established in order to correctly identify the AE or medication as occurring during treatment or not. For purposes of imputing missing components of partially-reported start and stop dates for AEs and for medication use, the algorithms listed below will be followed. Start and stop dates of AEs or concomitant medication will be displayed as reported in the subject data listings (i.e., no imputed values will be displayed in data listings).

Partial AE and concomitant medication start dates will be imputed as follows:

- If year is missing, no imputation will be performed.

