Primary Analysis: This study consists of a 12-week placebo-controlled, double-blind treatment period (Period 1), followed by a 24-week active treatment period (Period 2). When all subjects have completed or dropped out of Period 1, an unblinded analysis of the data collected from Period 1 can be conducted.

Follow-up Analysis: When all subjects have completed all of the Week 44 assessments or have dropped out of study, the follow-up analysis will be conducted on all data collected in the study.

B. Efficacy Endpoints

Primary efficacy endpoint

Primary efficacy endpoint is the proportion of subjects achieving Hidradenitis Suppurativa Clinical Response (HiSCR) at Week 12. A response is defined as a reduction of at least 50% in abscess and inflammatory nodule count (AN) count with no increase in abscess count and no increase in draining fistula count compared to baseline.

% Reduction from Baseline in AN Count
$$= 100 \times \frac{\text{(Baseline AN Count - Week 12 AN Count)}}{\text{Baseline AN Count}}$$

The proportion of subjects achieving HiSCR at Week 12 will be calculated as those subjects having % Reduction from Baseline in AN count \geq 50 and (Baseline Abscess Count — Week 12 Abscess Count \geq 0) and (Baseline Draining Fistula Count — Week 12 Draining Fistula Count) \geq 0 at Week 12 divided by the total number of subjects in each treatment group.

The location and extent of HS will be assessed at visits in the Time and Events Table by recording the anatomic location(s) of the disease, as well as the number of HS inflammatory nodules, abscesses, fistulae, and scars in each of the locations in the "Anatomic Location and Number of HS Lesions" CRF. Twelve body areas will be evaluated: left and right axillae, left and right inframammary areas, intermammary area, left and right buttocks, left and right

inguino-crural folds, perianal area, perineal area, and other. Total number of nodules, abscesses, fistulae, and scars for each subject will be calculated respectively by sum of the number across the locations.

Secondary Efficacy Endpoints

- Change from Baseline in total AN count at Week 12.
 Change from Baseline = Week 12 Count Baseline Count
- Proportion of subjects achieving at least 30% reduction and at least 1 unit reduction from Baseline in the subject's global assessment of skin pain (NRS30) in subjects with a Baseline NRS of at least 3, evaluated at Week 12.

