The following provides sample code for implementing the CMH analysis for 30 mg avacopan vs. placebo:

```
ods output commonpdiff=pdiff1;
proc freq data=test(where=(trt in (0, 2)));
```

where

- HS is the variable for Hurley Stage (Stage II vs. III)
- ANTIB is the variable for allowed antibiotics (Yes vs. No)
- ANTITNF anti-TNF drug use (Treatment naive vs. Previous treatment)
- TRT is the variable for treatment (0 for placebo; 1 for avacopan 10 mg; 2 for avacopan 30 mg)
- RESP is the response variable for achieving HiSCR at Week 12 (0 for No, 1 for Yes).

Missing assessments were handled with the use of NRI as the primary approach to handling missing data.

Sensitivity Analyses

Several sensitivity analyses will be conducted on the primary efficacy endpoint in the ITT1 Population. Each are described below:

1) Imputation of Missing Values with Multiple Imputation (MI) Analysis

The Multiple Imputation analysis will be carried out in three steps;

- Imputation of missing data. The imputation will be generated for the three components of HiSCR (abscess, draining fistula, inflammatory nodule counts). The variables to be included in the imputation model are: Baseline Hurley Stage, Baseline antibiotic therapy, Baseline anti-TNF-α treatment, treatment group, and values at each visit from Baseline up to Week 12. For each HiSCR component, 100 'complete' data sets will be generated using SAS PROC MI utilizing the MCMC algorithm. The seeds for the imputation will be specified as the value "12061", "36102", and "94218" for imputation of abscess, draining fistula, and inflammatory nodule counts, respectively. The 'complete' data sets for the individual components of the HiSCR will be merged by imputation number to allow calculation of the HiSCR and creation of 100 'complete' data sets for evaluation of HiSCR. Subjects who received concomitant anti-TNF-α treatment or other treatments with clinically relevant impact on HS will be forced as non-responders for all of 100 'complete' data sets.
- Analysis of imputed data sets. A CMH test, stratified by Baseline Hurley Stage (II vs. III), Baseline antibiotic therapy (Yes vs. No), Baseline anti-TNF-α treatment (Treatment naïve vs. Previous treatment) will be used to analyze each 'complete' HiSCR data set.

Synthesis of imputation and analysis results. SAS PROC MIANALYZE
will be used to generate the final estimate of the proportion difference
between avacopan and placebo groups and the corresponding 95%
confidence interval.

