PK parameters will be listed and summarized by treatment descriptively.

The derived PK parameters (C_{max}, AUC, T_{max} and C_{min}) will be rounded to three significant digits.

The relationship between PK parameters and efficacy endpoints such as HiSCR may also be evaluated.

G. Biomarker Assessments

A summary of the absolute and change from Baseline value for each available biomarker variable will be presented by treatment group, visit, and period.

A listing will be provided for subjects who have biomarker assessments.

H. Photographic Assessments

A listing will be provided for subjects who received photography by visit.

I. Supplementary Analyses Related to COVID-19

In order to describe the impact of COVID-19 on the current study, the following will be summarized in the tables/listings:

- Subjects discontinued from the study due to COVID-19 related on the study exit form.
- Add a new table for protocol deviations due to COVID-19.
- Add information for TEAE (COVID-19) in Overall AE summary table.
- Subjects with study visits missed or altered (including home health visit, phone/video conferencing, other) due to COVID-19. This may include altered or cancelled study visits and data collections because of a temporary study site closure during certain time periods of the COVID-19 pandemic.
 - An additional sensitivity analysis of the primary endpoint will be performed in the ITT population based on the LOCF and NRI imputation method.
 - LOCF: For any week 12 assessments performed via altered study visits or missing due to COVID019, last prior unaffected lesion assessment will be carried forward to week 12.

 NRI: impute any week 12 assessments performed via altered study visits or missing due to COVID019 as non-responders.

X. Changes from the Protocol Planned Analyses

The following changes from the protocol planned analyses are noted in this plan:

Changes	Protocol	SAP

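### The HiSCR multiple imputation draws lesion counts from separate normal models with no stated rounding or bounds, which pushes imputed subjects toward non-response

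*SAP*

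**What the plan says.** SAP VI.C names multiple imputation as a sensitivity method for the primary endpoint: "missing data in Period 1 are imputed based on the MCMC method", with details left to section VIII.D. There, the abscess, draining fistula and inflammatory nodule counts are imputed rather than the binary response, and 100 "data sets will be generated using SAS PROC MI utilizing the MCMC algorithm". Each count has its own seed, given "for imputation of abscess, draining fistula, and inflammatory nodule counts, respectively". The predictors are the three stratification factors, treatment group and the values at each visit from Baseline to Week 12. The completed "data sets for the individual components of the HiSCR will be merged by imputation number to allow calculation of the HiSCR". Subjects on anti-TNF or other relevant HS treatment are then set to non-response in every data set.

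The responder rule in SAP VIII.B is exact. It takes "Baseline Draining Fistula Count — Week 12 Draining Fistula Count" and requires the result to be at least 0. It does the same for abscesses and also requires a reduction of at least 50% in the combined abscess and nodule (AN) count.

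Neither section gives a rounding rule, a minimum or maximum, a transformation, or a rule for fractional or negative draws.

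**The concern.** PROC MI with MCMC draws from a multivariate normal model and neither rounds nor bounds the draws unless options are set. With a baseline count of 0, a draw of 0.2 is an increase and the subject fails HiSCR.

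Zero baselines are to be expected. Protocol 4.1 (criterion 5) can be met by nodules alone, and Protocol 4.2 (criterion 4) sets only an upper limit on draining fistulae. SAP III.A restricts percent change to subjects with at least one such lesion at baseline. The HS-PGA Moderate category in SAP VIII.B includes subjects with no abscesses and no draining fistulae.

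What is at stake is the value of MI as a robustness check. For the primary endpoint the SAP lists only NRI, MI and LOCF. Sensitivity analysis 2 is another non-responder rule, and the COVID-19 analyses in SAP IX.I use LOCF and NRI. MI is therefore the only model-based look at missing data. If an artefact pulls it toward NRI, agreement between the two will be read as more reassurance than it gives.

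**Working it through.** **Inputs from the documents.** SAP IV.C gives 130 per arm, HiSCR of 30% on placebo and 50% on avacopan, attrition of about 7% throughout the trial, and about 90% power. The documents give no count distributions and no figure for the MI.

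**The plan's related figure.** Power = Φ{[δ√n − 1.96√(2p̄q̄)]/√(p₁q₁ + p₂q₂)} with δ = 0.20 and p̄ = 0.40.
- n = 130: (2.280 − 1.358)/0.678 = 1.36, so power is 91.3%.
- n = 121 (130 × 0.93): (2.200 − 1.358)/0.678 = 1.24, so power is 89.3%.

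Both agree with the stated 90%.

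**Failure probability at a zero baseline.** For a normal draw with conditional mean μ and SD σ, P(draw > 0) = Φ(μ/σ).
- μ = 0: 50%.
- μ = 0.2, σ = 1: 58%.
- μ = 0.5, σ = 1.5: 63%.
- μ = 0.3, σ = 0.7: 67%.
- μ = 1, σ = 2: 69%.

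So half is the value at μ = 0, and a positive mean raises it. If both baselines are zero and each draw fails half the time independently, 1 − 0.5² = 75% fail.

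**Simulation.** Settings were 500 trials per scenario, 130 per arm, 5 imputations, monotone dropout after Week 2, and HiSCR tuned to 30% and 50%. The share of zero baselines per component was assumed to be 30% or 50%. Dropout was either completely random or related to the Week 2 AN count. At 7% missing, 7% × 130 ≈ 9 subjects per arm are imputed.

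Zero-baseline imputed subjects failed the no-increase rule in 51–56% of draws per component (true 4–6%; 25–36% after rounding and flooring at 0).

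HiSCR among imputed subjects, %, at 7% missing:

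| Scenario | True | MCMC, own counts | MCMC, all components' earlier counts | Own counts, rounded and floored | Joint predictive mean matching |
|---|---|---|---|---|---|
| 30% zero, random | 44.2 | 19.5 | 22.2 | 28.1 | 41.5 |
| 30% zero, related | 34.6 | 14.8 | 16.4 | 21.5 | 33.4 |
| 50% zero, random | 43.1 | 16.4 | 18.6 | 26.6 | 40.5 |
| 50% zero, related | 33.6 | 12.3 | 13.6 | 20.6 | 32.5 |

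The SAP does not say whether each run includes the other components' earlier values. The third and fourth columns show that this matters little.

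Effect on the average arm rate with own counts: 0.07 × (44.2 − 19.5) = 1.7 points in the first row, and 1.4, 1.9 and 1.5 points in the others.

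Shift in the 30 mg minus placebo difference, points, at 7% missing (SE at most 0.08 for MCMC with own counts):

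| Scenario | MCMC, own | MCMC, all | NRI | Predictive mean matching | MCMC own ÷ NRI |
|---|---|---|---|---|---|
| 30% zero, random | −0.73 | −0.70 | −1.54 | −0.38 | 47% |
| 30% zero, related | −0.40 | −0.44 | −1.01 | −0.24 | 40% |
| 50% zero, random | −0.82 | −0.83 | −1.52 | −0.43 | 54% |
| 50% zero, related | −0.52 | −0.56 | −0.97 | −0.42 | 54% |

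With the all-components version the ratio reaches 0.56/0.97 = 58%. As a check on the NRI column, random dropout of 7% should cost about 0.07 × 20 = 1.4 points.

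At 4% missing, MCMC with own counts shrinks the difference by 0.25–0.49 points. At 15% it shrinks it by 0.85–1.73, against 2.10–3.17 for NRI.

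**Other assumed counts.** A second simulation used 30–70% zero abscess baselines, 30–50% zero fistula baselines and higher new-lesion rates. It was not tuned to 30% and 50%. Zero-baseline failure was 57–66% per component, and 81–88% when both baselines were zero (true 16–58%). Imputed HiSCR was 8–14% against a true 22–30%, and the difference shrank by 0.3–0.6 points at 7% missing. A further run, also untuned and with zero-baseline shares of 15–50%, gave 51–53% abscess failure (true 5%) and shrinkage of 0.7–0.9 points against 1.7–2.0 for NRI. In that run joint predictive mean matching gave 60–63% imputed response against a true 63–66%, and rounding with flooring gave 44–48%.

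**The case against.** The strongest objection is size. The standard error of the difference is √(0.3 × 0.7/130 + 0.5 × 0.5/130) = 5.9 points, so a shift of 0.4–0.8 points is about 7–14% of one standard error. Predictive mean matching leaves 0.24–0.43 points, so the net gain on the difference is only 0.10–0.39 (for example 0.73 − 0.38 = 0.35). No change in a p-value or conclusion has been shown. The 7% covers the whole trial, so attrition by Week 12 may be lower. Some imputed subjects would be forced to non-response anyway, which the simulation settings do not include. The 15% case is an assumption, since SAP IX.I reports "Subjects with study visits missed or altered" but gives no rate. All of this stands.

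The magnitudes also depend on the assumed counts. With another set of counts, shrinkage at 7% missing fell from 0.57 points at a 50% zero-baseline share to 0.18 at a 5% share. In one untuned run (about 45% against 60% HiSCR) the difference hardly moved, although imputed response was 28–34% against a true 55%. This stands too, as a limit on the size but not on the mechanism or its direction.

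Finally, the SAP is silent on rounding rather than ruling it out, and a programmer could add options. In one check rounding and flooring cut the shrinkage to 0.09–0.28 points, so a simpler repair would serve the treatment contrast fairly well. It does not repair the imputed response itself, which stayed at 31–35% against a true 47%.

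**Conclusion.** The concern holds. Run as written, the MI understates HiSCR among imputed subjects by roughly half: 12–22% against 34–44% in the tuned simulation, and 8–14% against 22–30% under harsher assumptions. At 7% missing it shrinks the treatment difference by 0.4–0.8 points in the tuned scenarios and keeps 40–58% of the NRI shift. Another tuned set of counts gave 20–36%.

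The mechanism follows from the SAP text and the default behaviour of the procedure. The size rests on assumed count distributions, zero-baseline shares and dropout patterns. The bias is generally conservative for an efficacy claim, is small at the expected attrition and does not touch the primary NRI test. The harm is to interpretation: closeness of MI to NRI would partly reflect the imputation method, not robustness to missing data.

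**What to change.** Replace the MCMC step in SAP VIII.D with a single imputation model, and make the description in VI.C match. The model should hold all three counts at Baseline and Weeks 2, 4, 8 and 12, the three stratification factors, and treatment group as a categorical factor. Impute by arm only if the model is stable. Use predictive mean matching (PROC MI, FCS with REGPMM) so that every draw is an observed non-negative integer. Keep the 100 data sets, the forced non-response rule, the stratified CMH test and the MIANALYZE step.

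Rounding and flooring alone is a partial repair. If it is chosen instead, the SAP should state the rule and acknowledge the remaining bias.

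The cost is one SAP paragraph, a changed PROC MI statement and slightly more programming for a larger model (3 counts × 5 visits = 15 count variables). In the tuned simulation a residual shrinkage of 0.2–0.4 points remains at 7% missing. SAP I.A allows such a revision before the freeze of the Week 12 data.
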